#### 4.8.1.2. Sensitivity Analysis for Primary Efficacy Endpoint

The following sensitivity analyses will be performed:

- Repeat the primary efficacy analysis as described in Section 4.8.1.1 based on the PP Population.
- Compare the combined MORF-057 200 BID and 100 BID dose group with the placebo group based on the FAS.

Furthermore, if there is any discrepancy between the randomization stratum reported in the IRT and the actual stratum the participant belongs to, a sensitivity analysis for the primary endpoint will be performed using CMH method stratified by the randomization stratum reported in the IRT based on the FAS. Any discrepancies between the randomization stratum reported in IRT and the actual stratum will be summarized.

A summary of proportion of clinical remitters with stool frequency subscore 0 as well as 1 will be provided based on the FAS.

#### 4.8.2. Secondary Efficacy Endpoint Analysis

The secondary endpoint for this study is the proportion of participants with clinical response at Week 12 as determined using the mMCS: decrease from baseline in the mMCS  $\geq 2$  points and  $\geq 30\%$  from baseline, plus a decrease in rectal bleeding subscore  $\geq 1$  or an absolute rectal bleeding subscore  $\leq 1$ .

The clinical response rate will be analyzed based on FAS using CMH method stratified by randomization stratification factors (baseline MES [ $<3$  vs  $3$ ] and previous use of advanced therapy treatment [advanced therapy-naïve vs advanced therapy-experienced]) for comparison of each MORF-057 dose group with the placebo group, similar to the primary analysis performed for the primary endpoint. The p values will be provided. The point estimates of risk difference between groups, along with both 90% and 95% CIs will be computed based on the stratified risk difference using the Cochran-Mantel-Haenszel (CMH) weights. All participants with missing data for determination of endpoint status will be considered as a non responder in the analysis by using the NRI method.

Morphic Therapeutic, Inc.  
Study Number: MORF-057-202

Statistical Analysis Plan  
Version 1.0, 16SEP2024

Sensitivity analysis will be performed by repeating the secondary efficacy analysis using the PP Population. Additionally, another sensitivity analysis will compare the combined MORF-057 200 BID and 100 BID dose groups with the placebo group for FAS.

Furthermore, if there is any discrepancy between the randomization stratum reported in the IRT and the actual stratum the participant belongs to, a sensitivity analysis for the secondary endpoint will be performed using CMH method stratified by the randomization stratum reported in the IRT based on FAS.

#### 4.8.3. Exploratory Efficacy Endpoints Analysis

All exploratory efficacy endpoints will be summarized using the FAS, unless otherwise specified.

##### 4.8.3.1. Proportion-Based Exploratory Efficacy Endpoints

The proportion-based exploratory efficacy endpoints are listed in [Table 6](#) (see the definitions of endpoints in [Table 2](#) and the details of efficacy assessments in Section [6.3](#)).

**Table 6: Proportion-Based Exploratory Efficacy Endpoints**

Rate	Week2	Week 6	Week 12	Week 52	Week 104
Clinical remission				X	
Clinical response				X	
MCS remission			X	X	
MCS response			X	X	
Histologic remission by RHI			X	X	X
Histologic remission by NI			X	X	X
Histologic remission by Continuous Geboes			X	X	X
Histologic improvement by RHI			X	X	X
Endoscopic improvement			X	X	X
Endoscopic remission			X	X	X
Mucosal healing (endoscopic remission and histologic remission as determined using the RHI)			X	X	X
Mucosal improvement (endoscopic improvement and histologic improvement as determined using the RHI)			X	X	X
Symptomatic response	X	X			
Partial MCS response		X			
Corticosteroid-free remission				X	
Need for UC-related hospitalizations and surgeries			X	X	

#### Induction Period Analysis

The proportion-based exploratory endpoints (see for definition in [Table 2](#)) at Week 12, as outlined in [Table 6](#), will be included in the Induction Period Analysis and analyzed using CMH method stratified by randomization stratification factors for comparison of each MORF-057 dose group with the placebo group, similar to the primary efficacy analysis as described in [Section 4.8.1.1](#). The p-value will be calculated for exploratory use. The point estimates of risk difference between MORF-057 and placebo groups with 95% CI will be computed based on the stratified risk difference using the Cochran-Mantel-Haenszel (CMH) weights. All participants with missing data for determination of endpoint status will be considered as a non responder in the analysis by using the NRI method. Additionally, all these exploratory endpoints will also be summarized with the proportions and 95% CI for each treatment group by previous use of advanced therapy for UC (naïve vs experienced), by baseline MES score (<3 vs 3), and by baseline mMCS score ( $\leq 7$  or  $> 7$ ).

The proportion of participants with symptomatic response and the proportion of participants with partial MCS response will be summarized by treatment groups at each scheduled visit up to Week 12 inclusive, along with the 95% CI. The point estimates of risk difference between MORF-057 and placebo groups with 95% CI will be computed based on the stratified risk difference using the Cochran-Mantel-Haenszel (CMH) weights. The summaries will use the following two approaches:

- All randomized: at each visit, proportions for each treatment group will be calculated using the total number of participants in the FAS within that group as the denominator, and participants with missing data will be considered as non-responders by using the NRI method. The calculations will include the re-allocated EOT visits (See the re-allocation approach in [Section 2.3](#)) at that visit.
- As observed: at each visit, the denominator for calculating the proportions will be the number of participants with non-missing assessment at that visit, without including the re-allocated EOT visits and without using the NRI method.

In addition, the proportion of participants with symptomatic response and partial MCS response will also be summarized by treatment groups at each scheduled visit up to Week 12, along with the 95% CI, using the above two approaches for the following subgroups:

- Prior use of advanced therapy treatment (naïve vs experienced)
- Baseline MES score (<3 vs 3)

Line plots showing the proportion ( $\pm$  95% CI) at each of the scheduled visits will be provided for each treatment group, both for the overall population and for the above subgroups.

### **52-week Treatment Period Analysis and 104-week Total Treatment Period Analysis**

All proportion-based exploratory efficacy endpoints at Week 52 and Week 104, as outlined in [Table 6](#), will be summarized descriptively by treatment groups. The proportions, along with their corresponding 95% CIs, will be provided for the overall population, by previous use of advanced therapy for UC (naïve vs experienced), by baseline MES score (<3 vs 3), and by baseline mMCS score ( $\leq 7$  or  $> 7$ ). The denominator for calculating the proportions for each treatment group will be the total number of participants in the FAS within that group, except for the group initially randomized to placebo, which will use the total number of participants continuing to the Maintenance Period as the denominator.

In addition, the proportion of participants with symptomatic response and the proportion of participants with partial MCS response, along with the 95%CI, will be summarized by treatment groups at each

scheduled visit up to Week 52 in the 52-week Treatment Period Analysis and up to Week 104 in the 104-week Total Treatment Period Analysis. The summaries will use the following two approaches:

- All randomized: at each visit, proportions for each treatment group will be calculated using the total number of participants in the FAS within that group as the denominator, except for the group initially randomized to placebo, which will use the number of participants continuing to the Maintenance Period as the denominator. Participants with missing data will be considered as non-responders by using the NRI method. The calculations will include the re-allocated EOT visits (See the re-allocation approach in Section 2.3) at that visit.
- As observed: at each visit, the denominator for calculating the proportions will be the number of participants with non-missing assessment at that visit, without including the re-allocated EOT visits and without using the NRI method.

The above summaries for proportions of participants with symptomatic response and partial MCS response will also be provided for the subgroups by previous use of advanced therapy for UC (naïve vs experienced), and by baseline MES score (<3 vs 3), in both 52-week Treatment Period Analysis and 104-week Total Treatment Period Analysis. Line plots showing the proportion ( $\pm$  95% CI) at each of the scheduled visits will be provided for each treatment group, both for the overall population and for the subgroups.

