To assess the effect of MORF-057 on non-endoscopic biomarkers of inflammation at Weeks 12 and 52	
 
Change from baseline to Weeks 12 and 52 in high-sensitivity C-reactive protein (hs-CRP) levels
 
Change from baseline to Weeks 12 and 52 in fecal calprotectin levels
 

To evaluate the effect of MORF-057 on patient-reported outcomes (PROs) at Weeks 12 and 52	
 
Change from baseline to Weeks 12 and 52 in Inflammatory Bowel Disease Questionnaire (IBDQ) Score
 

To evaluate the effect of MORF-057 on corticosteroid-free remission at Week 52	
 
Proportion of participants in corticosteroid-free remission at Week 52, as determined using the mMCS, among the participants who were on a stable dose of corticosteroids at baseline
 

To characterize the effect of MORF-057 on the need for UC-related hospitalizations and surgeries	
 
Percentage of participants requiring UC-related hospitalization or surgery at Weeks 12 and 52
 

To evaluate the long-term histologic and endoscopic effects of MORF-057 at Week 104	
 
Proportion of participants in histologic remission at Week 104 as determined using the RHI
 
Proportion of participants in histologic remission at Week 104 as determined using the NI
 
Proportion of participants in histologic remission at Week 104 as determined using the Continuous Geboes Score
 
Proportion of participants with histologic improvement at Week 104 as determined using the RHI
 
Proportion of participants with endoscopic improvement at Week 104 as determined using the MES
 
Proportion of participants in endoscopic remission at Week 104 as determined using the MES
 
Proportion of participants in endoscopic remission as determined using the MES and histologic remission as determined using the RHI at Week 104
 
Proportion of participants with endoscopic improvement as determined using the MES and a histologic improvement as determined using the RHI at Week 104
 

Safety	
To assess the safety and tolerability of MORF-057	
 
Frequencies and proportions for TEAEs, treatment-emergent serious adverse events (TESAEs), and TEAEs leading to study drug discontinuation
 

Pharmacokinetics (PK)	

Objectives	Endpoints

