**Table 2: Efficacy Endpoints Definitions**

Term	Definition
Clinical remission	Determined using the mMCS: Rectal bleeding subscore of 0; a stool frequency subscore of $\leq 1$ ; and an MES of $\leq 1$ without friability.
Clinical response	Determined using the mMCS: Decrease from baseline in the mMCS $\geq 2$ points and $\geq 30\%$ from baseline, plus a decrease in rectal bleeding subscore $\geq 1$ or an absolute rectal bleeding subscore $\leq 1$
MCS remission	MCS $\leq 2$ and no subscore higher than 1
MCS response	Decrease in MCS $\geq 3$ points and $\geq 30\%$ from baseline, plus a decrease in rectal bleeding score $\geq 1$ or an absolute rectal bleeding score $\leq 1$
Histologic remission by RHI	RHI $\leq 3$ (with 0 for lamina propria neutrophils score and neutrophils in the epithelium score and without ulcers or erosions)
Histologic remission by NI	NI=0
Histologic remission by Continuous Geboes	Continuous Geboes $\leq 3$
Histologic improvement	$\geq 7$ -point reduction in RHI
Endoscopic improvement	MES $\leq 1$
Endoscopic remission	MES=0
Mucosal healing	MES=0 and RHI $\leq 3$ (with 0 for lamina propria neutrophils score and neutrophils in the epithelium score and without ulcers or erosions)
Mucosal improvement	MES $\leq 1$ and $\geq 7$ -point reduction in RHI
Symptomatic response	Decrease in Partial mMCS $\geq 1$ point and $\geq 30\%$ from baseline, plus a decrease in rectal bleeding subscore $\geq 1$ or an absolute rectal bleeding subscore $\leq 1$
Partial MCS response	Decrease in Partial MCS $\geq 2$ points and $\geq 30\%$ from baseline, plus a decrease in rectal bleeding subscore $\geq 1$ or an absolute rectal bleeding subscore $\leq 1$

Term	Definition
Time to symptomatic response	Time from randomization date to symptomatic response
Corticosteroid-free remission	Determined only in participants who were receiving corticosteroids on study Day 1. Includes such participants who are both in clinical remission (as determined using the mMCS) at Week 52 and off corticosteroids for $\geq 8$ consecutive weeks prior to Week 52.

Please see details of efficacy assessments in Section 6.3 of this document and Section 8.7 of the study protocol.

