### 1.3. Sample Size and Power

The sample size was determined based on the primary endpoint of clinical remission at Week 12 by using the Chi-Squared Test to compare two proportions. A sample size of 70 participants per group (giving a total of 280) will provide 80% power to detect a difference of 15% in the clinical remission rate between MORF-057 and placebo, based on the use of a two-sided test at the alpha=0.10 level of significance. The calculation is based upon an assumed placebo remission rate of 7%.

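### The full-FAS denominator set for all Week 52 proportions contradicts the definition of corticosteroid-free remission, which covers baseline corticosteroid users only

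*SAP*

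**What the plan says.** **Corticosteroid-free remission.** Table 1 defines the Week 52 endpoint "among the participants who were on a stable dose of corticosteroids at baseline". Table 2 says it is "Determined only in participants who were receiving corticosteroids on study Day 1". Table 6 marks it at Week 52. The 52-week and 104-week part of Section 4.8.3.1 covers all Table 6 endpoints at those weeks and states: "The denominator for calculating the proportions for each treatment group will be the total number of participants in the FAS within that group". It names one exception: the initial placebo group uses all participants continuing to Maintenance. Section 4.8.3.4 adds corticosteroid-free remission at Week 104 with a proportion and 95% CI, but no denominator.

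**UC-related hospitalization or surgery.** Table 6 lists "Need for UC-related hospitalizations and surgeries" at Weeks 12 and 52. For the Week 12 endpoints in Table 6, the Induction Period part of Section 4.8.3.1 says: "All participants with missing data for determination of endpoint status will be considered as a non responder in the analysis by using the NRI method". Section 2.4.3 sets the same rule for binary exploratory endpoints in general, subject to exceptions stated elsewhere. No section says what a responder is for this endpoint.

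**The concern.** Two programmers working from the same SAP could produce different corticosteroid-free remission tables. One following Section 4.8.3.1 divides by every FAS participant in the arm. One following Table 2 divides by corticosteroid users. The first table mixes the treatment result with the arm's share of users, and participants who were never on corticosteroids count as failures for an endpoint they could not meet. Corticosteroid use is not a stratification factor (Section 1.4.1 lists only baseline MES and prior advanced therapy), so the share can differ between arms by chance.

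For hospitalization or surgery, the event is the bad outcome. A rule that turns missing data into nonresponse is conservative only where response is the good outcome. Here it does not say which way the imputation goes.

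**Working it through.** **Plan's own figure.** The SAP gives no figure for either endpoint; its one calculation supplies the arm size used below. Section 1.3 states that 70 per group "will provide 80% power to detect a difference of 15% in the clinical remission rate", with a 7% placebo rate and a "two-sided test at the alpha=0.10 level of significance". For 7% versus 22%, with pooled variance under the null and no continuity correction:

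n = [1.645 × √(2 × 0.145 × 0.855) + 0.842 × √(0.07 × 0.93 + 0.22 × 0.78)]² / 0.15² ≈ 67.1, so 68 per group. Power with 70 per group is 81.5%. The plan's figure is reproduced.

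**Corticosteroid-free remission.** Let N be the denominator under Section 4.8.3.1, m the corticosteroid users among them, and x the successes. Then

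x/N = (x/m) × (m/N) = defined rate × share of users.

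The share of users is also the highest value x/N can take. The SAP gives neither the share nor the rate, so the inputs below are assumptions. N is 70. Half-widths are 1.96 × √(p(1 − p)/n), the normal approximation named in Section 4.

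| Assumed users m (share) | Successes x | x/m, per Table 2 | x/70, per Section 4.8.3.1 | Half-width on m | Half-width on 70 |
|---|---|---|---|---|---|
| 14 (20%) | 4 | 28.6% | 5.7% | 23.7 points | 5.4 points |
| 21 (30%) | 6 | 28.6% | 8.6% | 19.3 points | 6.6 points |
| 28 (40%) | 8 | 28.6% | 11.4% | 16.7 points | 7.5 points |
| 35 (50%) | 10 | 28.6% | 14.3% | 15.0 points | 8.2 points |

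All four rows have the same rate among users, yet the FAS figure runs from 5.7% to 14.3%. The interval is narrower in percentage points because participants with no endpoint status (49 of 70 in the second row) enter as certain failures.

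**Hospitalization or surgery.** Assume 4 recorded events in 70 and 14 participants (20%) with missing status:

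- missing = no event: 4/70 = 5.7%
- observed only: 4/56 = 7.1%
- missing = event: (4 + 14)/70 = 25.7%

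With 5% to 30% missing (4 to 21 participants), the first figure stays at 5.7%, the second runs from 6.1% to 8.2%, and the third from 11.4% to 35.7%.

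**The case against.** The best defence is that the specific definition governs. Section 4.8.3 applies the FAS to exploratory endpoints except where something else is specified, and Tables 1 and 2 do specify something else. An analyst might well restrict the denominator. That is plausible, but the proviso concerns the analysis set. The denominator sentence in the 52-week part of Section 4.8.3.1 carries no proviso and names a single exception, which does not mention corticosteroid users. Section 4.8 qualifies only the placebo group's denominator. The conflict stands.

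A reader might infer more than the SAP supports:

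- **That the nonresponder rule also contradicts corticosteroid-free remission.** It does not. Counting a corticosteroid user with missing data as a failure fits the definition; only the denominator conflicts.
- **That Section 4.8.3.1 fixes the wrong denominator at Week 104.** Table 6 does not mark this endpoint at Week 104. Section 4.8.3.4 adds it and is silent on the denominator.
- **That the FAS denominator is wrong for hospitalization or surgery.** It suits that endpoint.
- **That the hospitalization rate is bound to be wrong.** The event accumulates over a period, so a missed visit need not mean unknown status, and nothing in the SAP says dropouts count as hospitalized. Recorded events over the FAS equal the reading in which missing means no event. In the example this is 5.7% against 7.1% among those observed. The gap is an undefined direction, and its effect depends on how many statuses are missing.

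It is also fair that Week 52 results are descriptive, Week 12 exploratory p-values are for exploratory use, and neither endpoint is in the testing hierarchy of Section 4.8.6.

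**Conclusion.** The contradiction on corticosteroid-free remission at Week 52 holds. Applied literally, Section 4.8.3.1 reports the defined rate times the share of users: 0.2 to 0.5 of the defined rate under an assumed 20-50% share. It can make arms with equal rates among users look different and gives an interval that is too narrow in percentage points. The multiplicative relation follows from the SAP's text; its size rests on the assumed shares and rates. That both proportions must come out wrong would go too far: an analyst may let Table 2 prevail, and for hospitalization or surgery the finding is a missing rule. The primary and secondary tests and the sample size are untouched. The wording should be corrected before the Week 52 analysis.

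**What to change.** 1. In Section 4.8.3.1 for Week 52, and in Section 4.8.3.4 for Week 104, state that the denominator for corticosteroid-free remission is FAS participants receiving corticosteroids for UC at the randomization baseline. For the initial placebo group, use those of them who continue to Maintenance. Name the randomization baseline explicitly, because Sections 2.1.2 and 2.2 restart baseline and study days at the first maintenance dose for that group.
2. Reconcile Table 1 (a stable dose at baseline) with Table 2 (receiving corticosteroids on Day 1), so that one rule identifies the users. Section 4.3 already derives baseline corticosteroid use under blinded review.
3. Exempt UC-related hospitalization or surgery from the nonresponder rule. Count recorded events within each group's analysis period, keeping the FAS denominator (for the initial placebo group at Week 52, those continuing to Maintenance). For the 200 mg Q.D.-E group at Week 52 the period is Maintenance only, as Section 1.5.2 requires, so placebo-period events are not attributed to it. Add a Kaplan-Meier or exposure-adjusted summary to account for early exit.

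The cost is SAP wording and one further summary for hospitalization or surgery. The corticosteroid-free remission table will have a smaller n and a wider interval, which reflects the information available.

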#### 4.8.3.2. Continuous Exploratory Efficacy Endpoints

##### Induction Period Analysis

All the continuous exploratory efficacy endpoints expressed as change from baseline at Week 12 as defined in Section 1.1, including hs-CRP, fecal calprotectin, and IBDQ Score, will be included in the Induction Period Analysis and analyzed in the FAS using an analysis of covariance (ANCOVA) model with treatment and randomization stratification factors as factors and baseline values as a covariate. Any participant who was randomized under the wrong stratum by mistakes will be analyzed according to the actual stratum the participant belongs to. The least-squares means and standard errors with 95% CIs for both changes from baseline in each treatment group and differences between MORF-057 and placebo groups will be provided. P-values will also be calculated for the exploratory use. Participants who do not have the baseline value or the value at Week 12 will be excluded from the analysis.

Additionally, line plots showing mean values ( $\pm$  SE) at baseline and each of the scheduled visits up to Week 12 visit will be presented by treatment groups.

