## 2.3. Mapping Rules for Early Treatment Termination and Unscheduled Visits

If a participant discontinued from study drug prematurely, they will be encouraged to complete the end of treatment (EOT) Visit at the time of study drug discontinuation and the Safety Follow-up Visit (visit to occur 4 weeks after the last dose of study drug is received). In the analyses, the efficacy and safety parameters measured at the EOT Visit will be re-allocated according to the following rules:

- If the assessment date for a given parameter at the EOT Visit is closer to the previous scheduled study visit date (the scheduled study visits are the general visits specified in the Schedule of Activities in Section 1.2 of the study protocol) and this parameter is scheduled to be measured at that visit but there is no measurement, the EOT Visit for this parameter will be re-allocated to the previous scheduled study visit. This re-allocation will not apply if the EOT visit falls within the Maintenance Period and the previously scheduled study visit occurs during the Induction Period.
- If the assessment date for a given parameter at the EOT Visit is closer to the next scheduled study visit date and this parameter is scheduled to be measured at that visit but there is no measurement, the EOT Visit for this parameter will be re-allocated to the next scheduled study visit. This re-allocation will not apply if the EOT visit falls within the Induction Period and the next scheduled study visit occurs during the Maintenance Period.
- Otherwise, the EOT visit will remain unassigned to a nominal visit.

The above re-allocation of the EOT Visit will be performed for each efficacy and safety parameter based on its individual scheduled visits in the protocol. Please see Section 1.2 of the study protocol for the scheduled visits for each parameter to be measured.

In addition, any clinical laboratory parameters, vital signs, and ECG measured at the unscheduled visits will be re-allocated according to the same rules above.

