## 2.4. Missing Data

Unless otherwise specified, there will be no substitutions made to accommodate missing data points, and the observed cases, without imputation, will be used for the analyses.

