#### **2.4.3. Handling of Missing Data in Efficacy Analysis**

For analysis of primary and secondary efficacy endpoints and other binary exploratory efficacy endpoints, missing endpoint data will be imputed using a nonresponder imputation (NRI) method, unless otherwise specified. Participants will be considered nonresponders for the NRI analysis if they have missing clinical efficacy data at a time point of interest.

For continuous exploratory efficacy endpoints expressed as change from baseline at Week 12, the primary analysis will use the analysis of covariance (ANCOVA) model for comparing MORF-057 group with the placebo group. Participants who have missing baseline value or the value at Week 12 will be excluded from the analysis. The details are described in Section [4.8.3](#).

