For participants initially randomized into the placebo group during the Induction Period and subsequently switched to MORF-057 treatment (i.e., 200 mg Q.D.-E) during the Maintenance Period, unless otherwise specified, only the data collected during the Maintenance Period will be used in the 52-week Treatment Period Analysis to evaluate the effect of MORF-057 200 mg Q.D.-E. The data will be presented in the treatment group denoted by 200 mg Q.D.-E.

The data for the 104-week Total Treatment Period Analysis (see Section 1.5.3) will be presented by treatment groups similar to the 52-week Treatment Period Analysis described above, unless otherwise specified. All data during the 104-week Total Treatment Period will be used in the analysis for participants initially randomized to an active MORF-057 treatment group, and only the data during the Maintenance and Extension Periods will be used for participants initially randomized to placebo and subsequently switched to MORF-057 for maintenance treatment.

Unless otherwise specified, only scheduled visits including re-allocated visits (EOT or unscheduled visits, as described in Section 2.3) will be included in all by-visit analyses of efficacy and safety data. For the group of participants initially randomized to placebo and subsequently switched to MORF-057 for maintenance treatment, only the visits after Visit 5 (week 12) will be included in the by-visit analyses for the 52-week Treatment Period Analysis and the 104-week Total Treatment Period Analysis.

Data that are not summarized will be listed only. All data will be listed as collected for all randomized participants and will be ordered by randomized treatment group and visit if applicable.

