#### 4.8.3.4. Additional Exploratory Efficacy Analysis

Additional exploratory analysis will be performed for change from baseline to Week 12 in the mMCS score by using an analysis of covariance (ANCOVA) model with treatment and randomization stratification factors as factors and baseline values as a covariate. Any participant who was randomized under the wrong stratum by mistakes will be analyzed according to the actual stratum the participant belongs to. The least-squares means and standard errors with 95% CIs for both changes from baseline in each treatment group and differences between MORF-057 and placebo groups will be provided. P-values will also be calculated for the exploratory use. Participants who do not have the baseline value or the value at Week 12 will be excluded from the analysis. The change from baseline to Week 12 in the mMCS score will also be summarized descriptively for each treatment group by previous use of advanced therapy for UC (naïve vs experienced), by baseline MES score (<3 vs 3), and by baseline mMCS score ( $\leq 7$  or  $> 7$ ).

Summary statistics (mean and SD) for baseline value, observed values and changes from baseline at scheduled visits including re-allocated EOT visit (see Section 2.3) will be provided by treatment groups for the following additional continuous exploratory variables on observed cases:

- Stool frequency subscore
- Rectal bleeding subscore
- Partial mMCS

The summaries will be provided both for the overall population and for the subgroups by previous use of advanced therapy for UC (naïve vs experienced) and by baseline MES score (<3 vs 3). The summaries will be provided at each scheduled visit up to Week 12 visit in the Induction Period Analysis, up to Week 52 visit in the 52-week Treatment Period Analysis, and up to Week 104 visit in the 104-week Total Treatment Period Analysis. Line plots showing mean values ( $\pm$  SE) and mean changes from baseline ( $\pm$  SE) at each of the scheduled visits will also be presented by treatment groups, both for the overall population and for the subgroups.

For the histologic variables, i.e., RHI, NI, and continuous Geboes score, descriptive summaries will also be provided by treatment groups for change from baseline at Week 12 in the Induction Period Analysis,

for change from baseline at Week 52 in the 52-week Treatment Period Analysis, and for change from baseline at Week 104 in the 104-week Total Treatment Period Analysis.

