#### 4.8.5. Estimands and Intercurrent Events

The estimand corresponding to the primary efficacy endpoint evaluated the difference in the proportion of subjects in clinical remission at Week 12 for each MORF-057 dose versus placebo in the FAS population. For the intercurrent events of premature treatment discontinuation, participants were considered non-responders by using the NRI method. Other binary multiplicity-controlled efficacy endpoints used the same estimand as the primary endpoint.

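### The exploratory Week 12 ANCOVAs exclude FAS participants without a Week 12 value, which may bias the difference from placebo if missingness is outcome-related and differs by arm

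*SAP*

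**What the plan says.** SAP 4.8.3.2 compares each MORF-057 group with placebo on Week 12 change in hs-CRP, fecal calprotectin and IBDQ. The model is an ANCOVA with treatment, the stratification factors and baseline, described as an FAS analysis. The FAS (3.1) is everyone randomized and dosed. The same paragraph then narrows it: "Participants who do not have the baseline value or the value at Week 12 will be excluded from the analysis". Section 4.8.3.4 repeats the model and the exclusion for mMCS change. Section 2.4.3 states the rule for continuous endpoints generally: "Participants who have missing baseline value or the value at Week 12 will be excluded from the analysis". The default in 2.4 is that "the observed cases, without imputation, will be used for the analyses".

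One rule softens this. Under 2.3, if an early-termination assessment is closer in time to the next visit, and the parameter is due there but not measured, "the EOT Visit for this parameter will be re-allocated to the next scheduled study visit". Section 4 includes re-allocated visits in by-visit efficacy analyses by default. The ANCOVA text in 4.8.3.2 and 4.8.3.4 does not mention them, although the neighbouring descriptive summaries do.

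On status, 4.8.3.2 says "P-values will also be calculated for the exploratory use", and 4.8.6 keeps exploratory endpoints outside the testing hierarchy.

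**The concern.** The analysed set is defined by something that happens after randomization, namely having a Week 12 value. Baseline and strata are the only covariates, so what was seen at Weeks 2 and 6, or at an EOT visit not mapped to Week 12, does not enter the model.

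The SAP also treats the same person in two ways on the same score. For clinical response on the mMCS, a missing Week 12 result counts as failure (2.4.3, 4.8.2). For mMCS change, that person is removed. Symptomatic and partial MCS response get both a nonresponder and an as-observed version (4.8.3.1), whereas the change scores get only a complete-case analysis. No estimand, imputation or sensitivity analysis is given for them.

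At stake are four sets of least-squares differences, confidence intervals and exploratory p-values against placebo, reported with no check on what the exclusion does to them.

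**Working it through.** **The plan's own figure.** The SAP gives no SD, effect size or dropout rate for these endpoints. Its only design calculation (1.3) is for remission: 70 per group, 7% vs 22%, two-sided alpha 0.10, power 80%. With pooled rate 0.145:

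- null SE = sqrt(2 × 0.145 × 0.855 / 70) = 0.0595
- alternative SE = sqrt((0.07 × 0.93 + 0.22 × 0.78) / 70) = 0.0582
- power = Φ((0.15 − 1.645 × 0.0595) / 0.0582) = 81.5%

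The figure reproduces, but it says nothing about the ANCOVAs.

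**Who is excluded.** Visits fall at Weeks 2, 6 and 12 (1.2). If Week 6 is the previous visit, the cut for moving an EOT value to Week 12 is (6 + 12)/2 = Week 9. Section 2.3 defines scheduled visits as the general study visits, but also says the mapping is done by each parameter's own schedule. For a parameter measured only at baseline and Week 12, the second reading would put the cut near Week 6. The mMCS also needs the stool frequency and rectal bleeding subscores, which are summarized at every scheduled visit (4.8.3.4), so the Week 9 cut still applies to those components. EOT attendance is encouraged, not assured.

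**Size, under assumed inputs.** A simulation with 400,000 participants per arm used these assumptions:

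- true Week 12 difference −1.0 (placebo −1.0, active −2.0), residual SD 2, baseline slope −0.4;
- Week 6 to Week 12 residual correlation 0.6;
- dropout either random, or concentrated in those with the worst Week 6 or worst Week 12 change;
- either no dropouts or half of them kept by re-allocation, a kept value being set equal to the true Week 12 value.

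The complete-case ANCOVA (treatment, baseline) gave:

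| Dropout placebo / active | Driven by | None kept | Half kept |
|---|---|---|---|
| any pattern tried | chance | about −1.00 | about −1.00 |
| 10% / 10% | Week 6 or Week 12 | about −1.00 | about −1.00 |
| 15% / 5% | Week 6 | −0.83 (18% too small) | −0.92 (8%) |
| 15% / 5% | Week 12 | −0.70 (30%) | −0.87 (13%) |
| 20% / 10% | Week 6 | −0.84 (16%) | −0.93 (7%) |
| 20% / 10% | Week 12 | −0.72 (27%) | −0.89 (11%) |
| 10% / 15% | Week 6 | −1.08 (8% too large) | −1.03 (3%) |
| 10% / 15% | Week 12 | −1.15 (14%) | −1.06 (6%) |

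The equal-loss row is unbiased because removing the same worst fraction from two distributions of the same shape moves both means equally.

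**Against sampling error.** With SD 2 and 70 per arm, SE = 2 × sqrt(2/70) = 0.34. Shortfalls of 0.16 to 0.30 are about 0.5 to 0.9 SE. With half kept, 0.07 to 0.13 is about 0.2 to 0.4 SE.

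**The case against.** The case for leaving the text alone is that these are exploratory endpoints with exploratory p-values. The mMCS is already analysed on the full FAS, with missing counted as failure, as clinical response. Early symptom data are reported by visit and in the time-to-response analysis. Re-allocation keeps some discontinuers, and the plausible bias is below one standard error. All of this stands. It limits the consequence, but it leaves the four estimates unchecked.

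A reader might infer more than the documents support:

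- *That the estimates are biased.* The SAP gives no dropout rates or reasons. Random missingness, or equal outcome-related loss in both arms, produced no bias above.
- *That all early failures leave.* Section 2.3 retains those with an EOT value close enough to Week 12.
- *That equal losses overstate the effect.* This follows only if every dropout has exactly zero change. With true changes of −2.5 and −1.5 and 10% loss in each arm, −2.5/0.90 + 1.5/0.90 = −1.11 against −1.0. It is not general.
- *That the ANCOVAs contradict 4.8.5.* The sentence there, "For the intercurrent events of premature treatment discontinuation, participants were considered non-responders by using the NRI method", concerns the primary and other binary multiplicity-controlled endpoints. Table 1 has no mMCS-change objective; 1.6 lists that analysis as an addition.

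**Conclusion.** The point holds in conditional form. All four Week 12 change-score comparisons are complete-case, re-allocation repairs this only in part, and no alternative analysis is planned. If missingness is related to outcome and differs by arm, the difference from placebo may be too small or too large. Under the assumed inputs, outcome-related loss that was heavier on placebo gave 16-30% attenuation (7-13% with half kept), and loss that was heavier on active gave 8-14% overstatement (3-6% with half kept). The bias was about zero when missingness was random or loss was equal by the same mechanism.

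These figures illustrate an mMCS-like scale. They are not predictions for this trial, and none was derived for hs-CRP, fecal calprotectin or IBDQ. The half-kept figures are favourable, since each kept value equals the true Week 12 value. The primary and secondary conclusions are unaffected. This is an inexpensive improvement to exploratory analyses.

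**What to change.** In 2.4.3, 4.8.3.2 and 4.8.3.4:

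- Analyse all FAS participants who have a baseline value.
- For markers measured before Week 12, use an MMRM over the scheduled post-baseline visits up to Week 12, with treatment, visit, treatment-by-visit, strata, baseline and baseline-by-visit.
- For mMCS, and for any marker not measured before Week 12, use multiple imputation by arm, followed by the ANCOVA already specified. For mMCS, the predictors should include Partial mMCS at Weeks 2 and 6 and any EOT value.
- State whether re-allocated EOT values enter the Week 12 model, and which reading of the 2.3 visit rule applies.
- Keep the complete-case ANCOVA as a sensitivity analysis.

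The cost is SAP wording and some extra programming, with no new data. The price in assumptions is that missing at random must be stated for the new analyses. Which markers suit the MMRM depends on the protocol's schedule of activities. SAP 4.8.3.2 already plans plots at scheduled visits up to Week 12, but the SAP does not list the visits for each marker.
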